4.0 Study Design

4.1 *Describe and explain the study design (e.g. case-control, cross-sectional, ethnographic, experimental, interventional, longitudinal, observational).*

Response: This Veggie Van effectiveness and implementation study, funded by the NIH, will be overseen by Drs. [name], [name], Co-Investigator, [name], Co-Investigator, and [name], Co-Investigator. This study will be coordinated by project coordinators and staff at UB and UNC.

For Aim 2 of the study, all study related procedures will be carried out by UB staff.

Aim 2: After 9 qualified organizations* have been identified among applicants, we will randomize proposed MM sites (33 total across all partner organizations), to an intervention (MM program implementation) or comparison condition (extended planning). Randomization will be stratified within each organization so that each organization will have 2 intervention and 2 comparison sites. One organization will have 5 sites. The 5th site will allow for more thorough testing of protocol procedures. This ensures that study groups will be balanced at the organizational level. The condition for which each proposed MM location was selected will be communicated at the time of award. Organizations will communicate to intervention sites that they want to open a MM at that location within the next year. Organizations will communicate to comparison sites that they want to work with them on a food systems planning process to determine if a MM program is the right fit for their location. At the end of the year-long planning process with comparison sites, the organization and proposed MM site will decide together how to proceed (start a MM, apply for grant funding for a different project; etc.).

Both arms will undergo community engagement efforts that serve to both identify potential research participants and engage them in the planning for a MM. Intervention sites will work with a community advisory committee to develop an engagement plan to raise community awareness of the forthcoming MM. Comparison sites will work with a community advisory committee to engage community members in a food access planning process.

Both intervention and comparison sites will distribute sign-up forms as part of the community engagement process. UB staff will identify from the sign-up forms those interested in participating in the study. Consent will be obtained via phone. Phone surveys and in-person data collection will then be completed.

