Partner organizations will choose two sites they would start working with first based on timeline and readiness. These two sites will be paired for the purposes of randomization; one will be randomized to the mobile market site (intervention) and the other to the planning site (control). The same process will be used for the remaining pairs of sites as applicable. Partner organizations will run a mobile market following the Veggie Van model for at least one year at community sites randomized to the mobile market intervention. Planning sites partake in a year-long food access planning process to help determine if the surrounding community would benefit from a mobile market at that location. After one year, the partner and the planning site can decide to implement a mobile market, or another food access program based on community feedback gathered through the planning activities. Two months prior to the launch date of both the mobile market site and the planning site activities, partner organizations work jointly with community sites to engage the community to raise awareness of the mobile market and to recruit potential customers to participate in the Veggie Van Study.

Partner organizations will identify individuals who are interested in learning more about a mobile market in their community. To facilitate recruitment to the Veggie Van study, the partner and community site will utilize interest forms or sign-up sheets to collect community member contact information. If community members indicate interest in participating in the Veggie Van Study, the research team will contact them to screen, provide consent, and enroll into the study.

[figure not shown]
The goal is to recruit at least 30 participants at each of 32 proposed mobile market sites (960 total). Eligible individuals include those at least 18 years old, ability to speak English and/or Spanish, are the primary grocery shopper for their household, and live near or otherwise regularly frequent the community site. A threshold was established to ensure that market sites will be serving a predominantly lower-income community and that the study team is sampling from the appropriate target population. At least 60% of eligible sign-up forms are required to be from individuals that self-identify as receiving government assistance such as: the Supplemental Nutrition Assistance Program (SNAP), the Special Supplemental Nutrition Program for Women,

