Infants, and Children (WIC), Temporary Assistance for Needy Families (TANF), Medicaid, Work First, and/or housing assistance.

The intervention is an evidence-based model intended for mobile markets, the Veggie Van model. Informed by the social cognitive theory, the Veggie Van model was designed to address the multiple dimensions of access to fresh produce for lower-income and underserved communities: acceptability, availability, affordability, accessibility, and accommodation. The VV program also includes a cooking and nutrition education component to improve self-efficacy for finding, purchasing, and preparing fruits and vegetables (F&V). Lastly, acceptance of SNAP and participation in local incentive programs further increase affordability.

Data collection will take place at baseline (prior to market launch and planning activities) and approximately 12-month follow-up while the market is still in operation and the planning site has not yet started a market. Data will be collected from market and planning site participants through surveys, 24hr-dietary recalls, and an in-person data collection event (where available). Baseline and 12-month follow-up surveys will include dietary-related psychosocial measures. These surveys will be administered over the phone. The main individual-level outcome, change in F&V intake at 12 months, will be measured through four 24-hour recalls (2 at baseline and 2 at 12 months), which will be administered over the phone by trained interviewers. One recall at each time point will be from a weekday and the other from a weekend day. Recalls will be collected using the Nutrition Data Systems for Research (NDSR) computer-based software application. A participant will receive The Food Amounts Booklet via mail after the baseline survey to have as a visual reference for the 24-hour recalls. In addition to survey data, body mass index (BMI) and dermal carotenoids will be measured at in-person data collection events at baseline and 12 months. Figure 1 illustrates a flowchart of the sequence of study events including partner selection, site randomization, and participant study activities.

Figure 1: Study sequence and data collection events

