(race $p=.01$; income: $p=0.02$). Including the baseline values as a covariate in an analysis of covariance (ANCOVA) is known to be a more powerful test than a group comparison of baseline to post-intervention change (42, 43). ANCOVA is not distorted by regression towards the mean bias, whereas a change analysis is subject to that bias (42, 43). We also conducted a sensitivity analysis excluding extreme F&V reporters, defined as participants who had a change (increase or decrease) greater than 10 servings of F&V per day based on generating histograms and identifying outliers in the data distribution. We conducted additional analyses comparing change in F&V intake for those who reported ever purchasing from VV (VV users) to those who did not report shopping at VV (VV non-users), including delayed-intervention control participants. Due to major disruptions to VV operations in the beginning of the study period (2020), we also looked for differences among a sub-sample of sites that launched after the peak of COVID-19 related closures defined as launching in 2021 or later (i.e., post-covid sites). All secondary outcome analyses were conducted using GLMMs and controlled for baseline covariates of interest and clustering within sites.

Additional analyses by question set can be found below:

Question Set	Answer options	Variable Creation	Analysis Plan
Demographics (13) Weight is asked again at follow-up	various	Will combine categories with small numbers of respondents BMI: created from height and weight	
For all main outcomes we need to control for site and relevant demographic variables
 
 1. Descriptive 2. Will test for differences between Ix and Control groups and include any variables that differ as co-variates in outcome analyses 3. BMI is Aim 1 outcome- compare intervention and control at 6 and 12 months. We expect BMI to stay the same for intervention at 6 months and decrease at 12 months whereas control will increase over time.

NCI F&V Screener (11)*	Frequency (per day, week or month) plus Portion Size	See below for scoring	Aim 1 Outcome. We hypothesize an increase in F&V consumption for intervention compared to control at 6 months.

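### The post-covid analysis selects sites on their own launch year, without keeping randomised pairs whole or comparing with the 2020 sites, so it cannot show that the market effect differed by COVID period

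*SAP*

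**What the plan says.** SAP section 2 describes how sites are chosen and allocated. "Partner organizations will choose two sites they would start working with first based on timeline and readiness". Then: "These two sites will be paired for the purposes of randomization; one will be randomized to the mobile market site (intervention) and the other" becomes the control. Community engagement and recruitment begin "Two months prior to the launch date of both the mobile market site and the planning site activities", so launch comes after allocation. The Protocol (section 4.0) also has allocation known early: "The condition for which each proposed MM location was selected will be communicated at the time of award".

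SAP section 6 gives the reason for the extra analysis: "Due to major disruptions to VV operations in the beginning of the study period (2020"). It then says that differences were looked for in "a sub-sample of sites that launched after the peak of COVID-19 related closures defined as launching in 2021 or later (i.e., post-covid sites").

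Four things are not stated in either document:
- which event counts as the launch of a planning site;
- whether both members of a pair are kept or dropped together;
- any contrast between the 2021-or-later sites and the 2020 sites;
- any arm-by-launch-period interaction. Protocol section 17.1 plans interaction terms in general and gives organisations and community types as examples of moderators. It does not name launch period.

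**The concern.** Randomisation protects the comparison within a pair. A filter applied to each site's realised launch year can break that protection if the two members of a pair fall on different sides of the cut. The cut uses a date that could depend on arm, since the SAP's stated reason for the analysis is disruption of market operations, and only market sites operate a market during the trial year.

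The rule is also ambiguous for controls. A planning site has a start of planning activities and may have a market a year later, and SAP section 6 itself refers to control participants with a delayed intervention. Two analysts could date the same planning site differently and form different control groups.

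The second issue is interpretation. The subset exists because of COVID disruption, so its result will naturally be read as the effect without disruption, and set against the overall or 2020 result. An estimate from one part of the sites carries no test of whether the two parts differ.

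**Working it through.** **Inputs from SAP section 2.1:** SD of change 2.7 cups/day, ICC 0.08, 21 analysed participants per site, difference 1 cup/day, one-sided 0.05, 32 sites (16 pairs).

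**Assumptions:** The number of sites launching in 2021 or later is not given. I take K of 16 intact pairs as post-covid, with K from 6 to 12, and apply the sample-size section's one-sided level to the subset.

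**Step 1. Reproduce the plan's figure.** Design effect = 1 + (21 − 1) × 0.08 = 2.6. Variance of a site mean = 2.7² × 2.6 / 21 = 0.903. With J sites per arm, SE = √(0.903 × 2/J). For J = 12, SE = 0.388 and the noncentrality is 1/0.388 = 2.58. A one-sided t test on 22 df (critical value 1.717) has power 0.803. This matches the SAP's 0.80.

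**Step 2. Same true effect of 1 cup/day in both periods.** The subset (K pairs) and the remaining sites (16 − K pairs) are independent, so the chance of a significant subset with non-significant remaining sites is power(K) × [1 − power(16 − K)], each on 2J − 2 df.

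**Step 3. Interaction.** SE = √(SE² in subset + SE² in remainder). Power is for a true effect of 1 cup/day post-covid and 0 in 2020, one-sided, 28 df.

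| K post / remaining | SE post | Power post | SE remaining | Power remaining | Step 2 chance | Interaction SE | Interaction power |
|---|---|---|---|---|---|---|---|
| 6 / 10 | 0.549 | 0.52 | 0.425 | 0.73 | 0.14 | 0.69 | 0.41 |
| 8 / 8 | 0.475 | 0.64 | 0.475 | 0.64 | 0.23 | 0.67 | 0.42 |
| 10 / 6 | 0.425 | 0.73 | 0.549 | 0.52 | 0.35 | 0.69 | 0.41 |
| 12 / 4 | 0.388 | 0.80 | 0.672 | 0.37 | 0.50 | 0.78 | 0.35 |

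For example, at K = 12: 0.803 × (1 − 0.373) = 0.50.

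**Step 4. What a split pair would do, if there were any.** Suppose b of the K market sites in the subset have lost their paired control, and those sites differ by D cups/day in mean change from intact-pair sites for reasons unrelated to the market. The contrast then shifts by (b/K) × D. With K = 10 and b = 2, that is 0.2 × D: 0.10 cup/day for an assumed D of 0.5, and 0.20 for an assumed D of 1. With b = 0 it is zero. The documents give neither b nor D.

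**The case against.** **Pairs may never have been split.** SAP section 2 pairs sites by timeline and readiness and speaks of a single launch date for the market and the planning activities. If that date is shared, pairs enter or leave whole. Planning sites also rely on community engagement, advisory committees and in-person events, which closures could delay too. This stands. A reader might infer that delayed markets stayed in while their controls dropped out, and that the subset is biased by some fraction of a cup. The documents report no split pair, so that reading is not supported.

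**Baselines from the closure period.** A reader might also infer that post-covid sites widely carry 2020 baselines. Recruitment is tied to the two months before launch, so as planned this arises mainly for launches early in 2021.

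**The SAP makes no claim about COVID masking an effect.** It says only that differences were looked for. This stands too: the point concerns what the result can support. The Protocol's general provision for interactions could cover launch period, but neither document says it will be used for that.

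**Discordance with the all-sites result is rarer.** The 23% to 50% refers to subset against remaining sites. Under the same assumptions (normal approximation, K from 8 to 12), a significant subset with a non-significant all-sites result occurs about 1% of the time for a common 1 cup/day effect, and about 5% for a common 0.5 cup/day effect. That pattern is still not an estimate of the difference between periods.

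**An arm-independent date is not readily at hand.** If sites were allocated at award, around the Protocol's January 2020 update, classifying by randomisation date could make every pair early. No planned launch date set before allocation is shown to exist. This limits the choice of date rule but not the case for keeping pairs whole.

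**Conclusion.** The concern holds in a limited form. The filter is by site, on a post-randomisation date, with no dating rule for planning sites, no whole-pair requirement and no named comparison with 2020 sites. Any bias from split pairs is of unknown size and may be zero.

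The subset result alone cannot show that the effect differed by COVID period. An identical 1 cup/day effect produces the apparently divergent pattern about 23% to 50% of the time with 8 to 12 of 16 pairs post-covid, and 14% with 6. Those figures rest on the SAP's SD, ICC and 21 per site, on intact pairs, and on assumed splits.

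This is a secondary, exploratory analysis. A reader might infer that the trial's main result is in doubt. It is not, because the primary test uses all sites and does not involve the launch-year filter.

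**What to change.** - Classify period by randomised pair, and keep or drop pairs whole. Section 1 of the SAP and the Protocol give 33 sites, so classify the unpaired site by its organisation.
- State one date rule that applies identically to both arms, and say which event counts as launch at a planning site. If the rule uses a realised date, say so, since that is still after randomisation.
- Report how many pairs the site-level rule would have split. If none, say that; the matter of pair-splitting is then closed.
- Fit one model to all sites with arm, period and arm-by-period terms. Report the market effect in each period and the interaction, all with confidence intervals, and rest any statement about COVID on the interaction.
- Label the analysis exploratory.

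The cost is SAP wording, a review of site dates and two further model terms. A few sites may change group. The interaction will be imprecise: power is about 35% to 42% one-sided for a 1 cup/day difference with 6 to 12 of 16 pairs post-covid. With SE 0.67 to 0.78 and a t multiplier of 2.05 (28 df), a 95% interval would be roughly ±1.4 to ±1.6 cups/day. That width should be visible to the reader, and a subset-only report would hide it.

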4.3 Other Outcomes

Psychosocial measures – Self-efficacy

Self-efficacy to purchase, prepare and eat fresh F&V and will be measured with a 10-point Likert scale using a selection of items adapted from a study of shoppers where self-efficacy was shown to be correlated with nutrition behaviors and will serve as a comprehensive assessment of the effect of the educational intervention.

Psychosocial measures - Benefits (expectations)

Benefits (expectations) and barriers to eating F&V will be measured using a 4-point Likert scale (strongly agree, agree, disagree, strongly disagree) previously tested in lower-income adults which reflects common benefits/barriers found in the literature.

Psychosocial measures will be measured at baseline and 12 months.

5. Population to be Analyzed

To be eligible for the study, individuals had to be at least 18 years old, able to speak English and/or Spanish, be the primary grocery shopper for their household, and live near or otherwise regularly frequent the site. Individuals were ineligible if they were planning to leave the area or stop frequenting the site within the next year. To ensure that sites were predominantly serving lower-income community members and that the study team was sampling from the appropriate target population, a goal was set that at least 60% of eligible sign-ups are from individuals who self-report utilizing assistance programs (e.g., SNAP, WIC, TANF, Medicaid, Work First, and/or housing assistance).

6. Analyses

In order to test the impact of the VV intervention on change in F&V intake, we used generalized linear mixed model (GLMM) with random intercept to control for clustering within sites. In order to further explore the intervention effect, we fit GLMMs that adjust for (1) baseline dietary intake and (2) race and baseline income due to significant differences between groups at baseline

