F&V 2-question*	Servings per day	Continuous	Aim 1 Outcome. We hypothesize an increase in F&V consumption for intervention compared to control at 6 months and that differences will be maintained at 12 months. We want to compare the 2 F&V measures and possibly combine them as was done in NC Strides and other projects
NHANES FFQ-Sweets (7)*	Frequency (per day, week or month)	1. Convert all answers to per day or per week depending on which seems more reasonable. 1 month=4.348 weeks 1 week=7 days 2. Sum all 7 questions to get a combine servings per (week or day) score	Aim 1 Outcome. We hypothesize a decrease in sweet consumption for intervention compared to control at 6 months.
Barriers to F&V (12)*	Strongly agree (1) Agree (2) Disagree (3) Strongly disagree (4) Don't know (5)	Answers 5, 6 and 7 will be treated as missing If answers are normally distributed, we will combine 1&2 and 3&4 and create a dichotomous variable. If answers are weight to one end or the other,	Descriptive Correlate with F&V consumption at each timepoint Mediator of F&V consumption

	Skip refuse (6) N/A (7)	we will look at them as 4-category variables or combine categories as is appropriate	
Shopping Behavior (10)* 2 questions repeated at follow-up	Various	
Will combine categories with small numbers of respondents (q65)
 
 - mark 6 and 7- skip/refuse as missing for baseline and follow-up - for everyone else, subtract follow-up from baseline - If number is positive then re-categorize as 1= shopping more often - If number is negative then re-categorize as 2= shopping less often - if number is 0, re-categorize as 3= shopping the same frequency 	
Descriptive at baseline
 
For questions available at follow-up:
 
(q65) Percent of people who shop more often, less often or the same at each type of store
 
 - Compare intervention vs. control percentages 
(q66 follow-up) calculate percent of people who answer “Veggie Van” as one of the stores they most shop at- compare intervention vs. control percentages

Importance to buy/make/eat F&V (1)*	5- point likert scale	If answer= 6 (don't know) or 7 (skip/ refuse), categorize as missing and treat remaining as continuous variable	
Descriptive
 
Correlate with F&V consumption at each timepoint
 
Mediator of F&V consumption

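### The SAP lets the observed answers decide how the 12 barriers items are coded, and collapses them to agree/disagree when a four-level coding would work well

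*SAP*

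**What the plan says.** SAP Section 4.3 (Other Outcomes) introduces the measure: "Benefits (expectations) and barriers to eating F&V will be measured using a 4-point Likert scale", taken at baseline and 12 months.

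The question-set table in SAP Section 6 then gives the coding of the 12 barriers items. Don't-know, refused and not-applicable answers become missing. For the rest there are two branches:

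- **Answers look normal:** "If answers are normally distributed, we will combine 1&2 and 3&4 and create a dichotomous variable".
- **Answers are skewed:** "If answers are weight to one end or the other", then "we will look at them as 4-category variables or combine categories as is appropriate".

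The analysis column for this row lists description, correlation with F&V consumption at each time point, and the role "Mediator of F&V consumption". It lists no comparison between arms.

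In the same table, the single importance item has the same three analyses but is treated as continuous once missing codes are removed. Both self-efficacy sets are also treated as continuous, and the SAP asks for a factor analysis to decide whether their items form a scale.

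**The concern.** A four-level item with a roughly bell-shaped spread is easy to analyse as a 1–4 score or with an ordinal model. That is the case in which the SAP reduces it to two levels, and it gives no reason. Strong and mild agreement become the same answer, so the item carries less information about anything it is related to.

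The coding is also not fixed in advance:

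- The SAP does not say how normality is judged, and a four-category item cannot be normal in any literal sense.
- It does not say whether the judgement is made per item or for all 12, at baseline or at follow-up. Items, or the two time points of one item, could end up coded differently.
- The skewed branch is open-ended.

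At stake are the correlations with F&V intake and the mediation analysis. A coarsened mediator tends to show a weaker link with the outcome, so an indirect effect would tend to be understated.

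**Working it through.** The plan gives no power, effect size or distribution for the barriers items, so there is no figure of its own to reproduce. The calculation asks how much information the collapse removes under assumed answer patterns.

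**Inputs from the SAP.** 12 items; four ordered categories; collapse 1 and 2 against 3 and 4 (Section 6 table).

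**Assumptions.** Each answer is an underlying normal variable cut at three points. The answer percentages are mine.

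**Formula, per item.** For a small shift, a category with probability p between cut-points a and b contributes (φ(a) − φ(b))² / p, where φ is the standard normal density. A fully observed normal variable has information 1.

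**Worked case, answers 16/34/34/16%.** Cut-points are about −0.99, 0 and 0.99, with densities 0.2433, 0.3989 and 0.2433.

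- Four categories: 2 × [0.2433²/0.16 + (0.3989 − 0.2433)²/0.34] = 2 × [0.370 + 0.071] = 0.882.
- Two categories: 2 × 0.3989²/0.50 = 0.637.
- Loss: 1 − 0.637/0.882 = 28%.

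**Other patterns, same formula.**

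| Answers (%) | Four categories | Two categories | Loss |
|---|---|---|---|
| 10/30/40/20 | 0.876 | 0.622 | 29% |
| 16/34/34/16 | 0.882 | 0.637 | 28% |
| 10/40/40/10 | 0.866 | 0.637 | 26% |
| 7/43/43/7 | 0.84 | 0.637 | 24% |
| 5/45/45/5 | 0.814 | 0.637 | 22% |
| 2/48/48/2 (middle pile-up) | 0.746 | 0.637 | 15% |
| 3/12/45/40 (skewed) | 0.807 | 0.426 | 47% |

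A plain 1–4 score does almost as well as the full four-category information (0.881 against 0.882 in the worked case), so nothing elaborate is needed to keep it.

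**Effect on a correlation.** Under the same model the correlation shrinks by the square root of the information ratio. A loss of 22 to 29% gives √0.78 = 0.88 to √0.71 = 0.84, so correlations are about 12 to 16% smaller.

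**If the 12 items are summed.** Assume one common factor and a common underlying inter-item correlation ρ. The efficiency of a sum is proportional to m²/V. Here m is the mean shift per item (the sum of φ over the cut-points used) and V = 12v + 132c, with v the item variance and c the covariance between two items. For 16/34/34/16 and ρ = 0.3:

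- Four-level sum: m = 0.3989 + 2 × 0.2433 = 0.8855; v = 0.89; c = 0.236; V = 10.68 + 31.15 = 41.83; m²/V = 0.01874.
- Sum of yes/no items: m = 0.3989; v = 0.25; c = arcsin(0.3)/2π = 0.0485; V = 3 + 6.40 = 9.40; m²/V = 0.01693.
- Loss: 1 − 0.01693/0.01874 = about 10%.

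For ρ from 0.2 to 0.5 and answers 16/34/34/16 or 10/40/40/10, the loss is about 9 to 12%. If instead a summed score were itself split at its median, simulation gives a loss of about 34 to 38%. The SAP does not say whether the items are summed. Its recode reads as item by item.

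**The case against.** The case for leaving the rule alone has several parts.

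- **The cost depends on the level of analysis.** A reader might infer that the barriers scale as a whole loses a quarter of its information. The documents do not support that. The figure is per item, under an assumed distribution, and drops to about 9 to 12% for a sum. This stands and limits the claim.
- **The branches are not reversed.** A reader might infer that the SAP dichotomises in the wrong case. In fact a midpoint split costs least when answers are symmetric and about 47% under the skewed pattern above, so avoiding it under skew is sensible. Nor is collapsing confined to the normal case, since the skewed branch permits it too. This stands. The fault is that collapsing is unnecessary and depends on the data.
- **The cut is natural.** In the normal branch it is fixed at the agree/disagree boundary. That is true, but the choice of branch and the whole skewed branch remain open.
- **No arm comparison is listed.** A reader might turn the loss into a drop in the trial's power. The row names no between-arm test, the documents give no effect size for barriers, and any such figure would have to allow for clustering by site.
- **The consequence is small.** Barriers sit under Other Outcomes. They are not named in the protocol's endpoints (Section 2.1) or in its mediation plan (Section 17.1). This stands.
- **The table has larger problems.** It refers to 6-month results, although SAP Section 2 schedules data collection at baseline and about 12 months only. That is a reason to revise the table as a whole. It does not justify this row.

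The SAP is dated February 2025 and already reports baseline p-values, so a reader might also infer that the barriers coding was chosen after looking at the answers. The documents do not show this; the row is written in the future tense.

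**Conclusion.** The point holds as a minor one. The SAP lets the observed distribution choose the coding of the barriers items, states no criterion, and dichotomises where a four-level coding would serve. It does so without a reason and unlike the comparable importance and self-efficacy items.

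The loss is about 22 to 29% per item for roughly symmetric answers, 15% with an extreme middle pile-up, and about 9 to 12% for a sum of dichotomised items. All of these rest on an assumed underlying normal variable and assumed answer percentages. The sum also assumes a common inter-item correlation.

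The effect is on the correlation and mediation analyses of an outcome listed under Other Outcomes. The direction for mediation (towards a smaller indirect effect) is a general expectation; its size was not calculated. The primary F&V analysis and its power are not affected.

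**What to change.** Delete the distribution-dependent rule and state one coding that applies whatever the answers look like:

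- **Item level:** keep the four ordered categories, analysed with an ordinal model or as a 1–4 score.
- **Scale level, if wanted:** a mean 1–4 score, provided the factor-analysis check that the SAP applies to self-efficacy supports a single scale. SAP Section 4.3 groups benefits with barriers, so reverse-code any benefit items or score them separately. State the minimum number of answered items for a score, since three response codes become missing.
- **Any comparison of arms:** a baseline-adjusted model with clustering by site.
- **Agree/disagree percentages:** descriptive only.

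If the analyses have already been run with collapsed categories, report both codings and label the split as chosen after the data were seen, where that is so.

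The cost is SAP wording and some re-analysis, with no new data. The small downside is that a mean or ordinal result is somewhat less simple to report than the percentage agreeing.
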